#### **Risks Related to Being in the Study**

This study has risks. Some of these risks we know about. There is also a possibility of risks that we do not know about that have not been seen in study participants to date. Some can be managed. Please call the study doctor if you have any side effects even if you do not think they have anything to do with this study. The risks we know of are:

- a) MRI risks: There are few potential risks of having an MRI scan, as it is a non-invasive procedure and does not involve any radiation. The main potential risk comes from loose metal objects, which, if taken near the scanner, could be dangerous. The combination of the noise of the scanner and confined space can also be stressful for people who feel uncomfortable in closed spaces.

- b) Blood draw risks: Drawing blood may cause very mild pain, bruising, redness, and rarely infection at the needle stick.
- c) Other risks: In addition to medical risks, being in this study may make you feel uncomfortable. You will be asked personal questions about your psychiatric and medical history. You may refuse to answer questions or stop the interview at any time if there is any discomfort. Administering the cognitive testing may sometimes be frustrating particularly if you are not performing as well as you think you should, and may also lead to mild mental and physical fatigue.

### **Benefits to Being in the Study**

You may or may not receive any direct benefit from being in this study. Information learned from this study may help other people with mood disorders in the future.

### **Timeline**

It is estimated that it will require approximately 3-5 months to recruit.

### **Primary and Secondary Outcome Measures**

The **primary outcome measure** in this study will be the association between performance on the EEfRT, MID, and PRT. Anthropometric data will be obtained from all participants at the day of the EEfRT assessment. Body mass index (BMI) will be measured using the formula  $BMI = \text{weight (Kg)} / \text{height (meters)}^2$ . The **secondary outcome** will be the association between the EEfRT/ MID/PRT and function reciprocity of the reward circuit/cognitive control network as measured by MRI/DTI. All participants will also have whole blood samples collected after a 12 hour fast. Metabolic parameters will be measured immediately in a single laboratory with the same assay. Insulin resistance and beta-cell function (i.e. insulin secretion) in basal state will be calculated from fasting plasma glucose and fasting insulin using the HOMA2 calculator (<http://www.dtu.ox.ac.uk>).

## Effort Expenditure for Rewards Task (EEfRT), Probabilistic Rewards Task (PRT), and Monetary Incentive Delay (MID) task

The EEfRT measures participants' willingness to make efforts to obtain a monetary reward under different conditions of reward probability and magnitude. In each EEfRT trial, participants are given an opportunity to choose between two tasks with different levels of difficulty: "hard task" and "easy task." Successful completion of the easy task trials requires 30 button presses using the dominant index finger within 7 seconds, whereas the hard task trials requires 100 button presses using the non-dominant little finger within 21 seconds. Participants will be informed that successful trial completion does not guarantee winning the monetary reward. Before making a choice, participants are provided with information that varies from trial to trial regarding: (1) the probability (12%, 50%, or 88%) of winning the money; and (2) the magnitude of reward for successfully completing the hard task. The reward magnitude will be set at \$1.00 for easy tasks and higher amounts that will vary per trial within a range of \$1.24-\$4.30 for hard tasks. Probability levels will always be applied to both the hard task and easy task, and there will be equal proportions of each probability level across the experiment. Participants are given 20 minutes to perform the task; thus, the number of trials will vary across the participants. The Probabilistic Rewards Task (PRT) measures response bias and sensitivity to reward under variable conditions. The Monetary Incentive Delay (MID) task assesses the basis of anticipation and consumption of reward and punishment. Each test takes approximately 20 minutes to administer.

### **Statistical Analysis**

Graph theoretical analysis (GTA) will be used to assess functional connectivity of the default mode network, cognitive control network, affect network and reward network. This is a

preliminary exploratory analysis, descriptive statistics will be conducted on the sociodemographic, clinical and metabolic parameters. Associations between obesity and alterations in functional connectivity will be the primary outcome of interest and additional coprimary outcome is the association between obesity and reward motivation as indexed by the EEfRT/MID/PRT task. Laboratory parameters will be used to explore potential mediational relationships between obesity and brain connectivity measurements, as well as reward performance.

For each variable, distribution normality will be assessed with one-sample Kolmogorov-Smirnov tests. Comparisons between groups will be conducted using independent samples t-tests and Mann-Whitney U (for normally and non-normally distributed variables, respectively). Participants are given 20 minutes to complete the EEfRT, and the number of trials completed during that time will vary among them (Table 1). Consistently with previous studies, only the first 50 trials will be used. Similar to previous studies using the EEfRT, we will use generalized estimating equation (GEE) models to test the effects of groups, reward magnitude and probability on the willingness to expend effort for rewards (i.e. percentage of trials on which the 'hard' task was selected). We will use an independent matrix, which best fit our data, and a binary logistic distribution to model the dichotomous outcome of choosing the hard versus the easy task. All GEE models will include reward magnitude, probability, and expected value (EV, defined as the interaction between reward probability and magnitude). In addition, each model will include a trial number as a covariate to control for possible effects of fatigue over the course of the task. Reward magnitude will be categorized in three groups: low (<\$2.30), medium (\$2.31-\$3.29), and high (>\$3.30). To assess associations between EEfRT and clinical and metabolic data, we will calculate the mean proportions of hard-task choices for all subjects.

Stepwise linear regression will then be used to identify significant predictors. MRI/DTI will be attained for all subjects.

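### The Statistical Analysis section ranks obesity versus connectivity as primary, which no other section does, and its EEfRT model tests undefined groups in a one-cohort study, so it gives no obesity estimate

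*Combined protocol and SAP*

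**What the plan says.** **Primary outcome.** The Statistical Analysis section says "Associations between obesity and alterations in functional connectivity will be the primary outcome of interest". It then adds that an "additional coprimary outcome is the association between obesity and reward motivation as indexed by the EEfRT/MID/PRT task". The Study Synopsis gives obesity versus performance on the reward paradigms as the primary aim. The Introduction gives obesity versus EEfRT effort as primary and EEfRT versus MRI/DTI as secondary. In Primary and Secondary Outcome Measures, the primary outcome measure "in this study will be the association between performance on the EEfRT, MID, and PRT", with no obesity or BMI term, and tasks versus MRI/DTI is secondary.

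**Analysis.** Also in Statistical Analysis, GEE models are planned "to test the effects of groups, reward magnitude and probability on the willingness to expend effort for rewards". Separately, "Comparisons between groups will be conducted using independent samples t-tests and Mann-Whitney U". To relate EEfRT to clinical and metabolic data, "we will calculate the mean proportions of hard-task choices for all subjects", after which "Stepwise linear regression will then be used to identify significant predictors". The section calls itself a "preliminary exploratory analysis".

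**Design.** Methodology, Participants, enrols 20 subjects with obesity, excludes BMI above 45, and admits major depressive disorder or bipolar I/II. No comparator is planned.

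**The concern.** There are two linked problems. First, the section that governs the analysis puts at the top an association that the other sections do not rank. A positive connectivity result with null task results, or the reverse, could each be reported as the primary finding by pointing to one section or another. The co-primary wording does not say whether one or both must succeed.

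Second, the scientific question is about obesity, yet the main EEfRT model asks about groups. If everyone enrolled has obesity and no groups are defined, that term has no meaning. The terms the plan says every GEE will contain (reward magnitude, probability, their interaction and trial number) do not include BMI. The model could be fitted exactly as described and leave the obesity question unanswered.

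**Working it through.** **1. Sections side by side**

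| Section | Ranked primary | Where imaging sits |
|---|---|---|
| Study Synopsis | Obesity vs the reward tasks | Opens with a brain-substrate aim; task vs connectivity appears in a broken sentence of unclear rank |
| Introduction | Obesity vs EEfRT; the hypothesis covers every paradigm | EEfRT vs MRI/DTI, secondary |
| Outcome Measures | The three tasks, no exposure named | Tasks vs MRI/DTI, secondary |
| Statistical Analysis | Obesity vs connectivity; obesity vs three tasks co-primary | Obesity vs connectivity, primary |

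Only the last row ranks obesity versus connectivity. Where other sections rank imaging, they pair it with task performance, which is a different association.

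**2. What the groups could be**
- Not obese versus non-obese: all 20 participants have obesity.
- Not the three reward-magnitude categories: magnitude is listed beside groups as a separate effect.
- Not BMI strata: no cut-point is given.
- Possibly MDD versus bipolar, since both are eligible. No section says so, and that contrast would not estimate an obesity effect.

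**3. Size of the ambiguity (illustration)**
The plan states no alpha, so two-sided 0.05 per test is assumed. For k independent tests of which any may succeed, the chance of at least one false positive is 1 − 0.95^k.
- One named primary: 0.05.
- Two co-primaries, each a single test: 1 − 0.95² = 0.0975. If both must succeed: 0.05² = 0.0025.
- One connectivity test plus three tasks (k = 4): 0.186.
- Four networks plus three tasks (k = 7): 0.302.

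Correlation between outcomes softens this. For two outcomes tested against BMI at n = 20 (200,000 simulated datasets), outcome correlations of 0.3, 0.5 and 0.7 gave 0.095, 0.091 and 0.084 if either counts, and 0.0045, 0.0086 and 0.016 if both must succeed. The 9.75% is the lower illustration for this plan, because it treats each co-primary as a single test.

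**4. Would a BMI term work with 20 participants?**
From the plan: 20 people, first 50 trials, probabilities 12/50/88%, magnitudes $1.24 to $4.30 in three categories, the interaction, trial number, independence working matrix. Assumed: between-person SD of 0.5, 1.0 or 1.5 on the logit scale; BMI either uniform on 30 to 45 or right-skewed (30 plus an exponential with mean 4, cut at 45); assumed trial-effect sizes. Across settings and repeated simulations:

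| EEfRT test of BMI | Rejection of a true null (nominal 5%) | Power, true correlation 0.5 between BMI and hard-task propensity |
|---|---|---|
| GEE, uncorrected robust z | about 10–12% | not comparable, since the test is oversized |
| GEE, Mancl-DeRouen variance, t on 18 df | 3.7–5.5% | 41–55% |
| Linear regression of mean hard-task proportion on BMI | 4.3–5.4% | 42–62% |

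Both valid routes have modest and similar power. The regression uses a summary the plan already computes.

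**The case against.** The strongest reply is that this is a pilot whose analysis is labelled exploratory, so strict error control is not required. That stands: the documents do not oblige family-wise control, and the percentages above are illustrations rather than breaches. The label does not say which result is primary, however, and the plan itself uses the words primary and co-primary.

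A reader might infer more than the text supports in four places.
- *That nothing in the plan could estimate an obesity association.* This goes too far. The stepwise regression on mean hard-task proportions could include BMI, which is measured on the day of the EEfRT, and the planned mediation analyses presuppose an obesity association. What the text lacks is a designation: no candidate predictors are listed, stepwise selection can drop BMI, and neither analysis is named as the primary test.
- *That the task set is equally in conflict.* Three sections name all three tasks. Only the Introduction's aim names EEfRT alone, and its own hypothesis covers every paradigm. This is a lesser discrepancy. The missing exposure in Outcome Measures is probably a dropped phrase.
- *That groups is simply an error for BMI.* MDD versus bipolar may have been meant. The documents neither say so nor rule it out, so the term should be described as undefined.
- *That a corrected GEE is the only sound analysis.* It is one option. Ordinary regression on the participant-level proportion holds its level at n = 20 without any correction.

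**Conclusion.** The plan is wrong as written on two counts and should be fixed. The primary outcome differs between the Statistical Analysis section and the other three, with no rule for the co-primaries. The EEfRT GEE and the two-sample tests rest on undefined groups in a single cohort, so the model as described yields no obesity estimate. These conclusions come from the text alone and need no assumption.

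The sizes are conditional. The 9.75% assumes two-sided 0.05, independence, one test per co-primary and success on either. It rises to 18.6% or 30.2% when the tasks, or the tasks and networks, are counted separately. The rejection rates and power in step 4 rest on the assumed between-person variation, BMI distribution and trial effects.

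**What to change.** Before outcome data are examined:

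1. **Name one primary outcome** and state it identically in the Synopsis, Introduction, Outcome Measures and Statistical Analysis sections, with BMI as the exposure in Outcome Measures. The choice is the investigators'. Rank every other association (BMI vs connectivity, task vs connectivity, task vs food diary or calorimetry) as secondary or exploratory, reported with 95% confidence intervals. If more than one primary is kept, state whether one or all must succeed.
2. **Make continuous BMI, forced into the model, the EEfRT test.** Use either (a) linear regression of each participant's mean hard-task proportion on BMI, which is already close to the plan, or (b) the planned GEE with BMI in place of or alongside groups and a small-sample variance correction, for example Mancl-DeRouen with t on 18 df. State alpha and sidedness. State that stepwise selection is exploratory.
3. **Define groups** (for example MDD versus bipolar) as a secondary contrast, or delete the between-group tests.

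Cost: wording in four sections, one model term and, under (b), a corrected variance. Outcomes not chosen lose primary status. No new data or visits are needed.

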## Methodology

### Participants

Participants will be identified at the Brain and Cognition Discovery Foundation (BCDF). Twenty subjects with obesity, will be enrolled. All patients will be assessed for concurrent psychiatric disorders (e.g. mood disorders). Eligibility criteria are as follows: inclusion criteria: (a) 18-65 years of age; (b) meeting DSM-V criteria for: (i) major depressive disorder (symptomatic or asymptomatic in any phase of the illness) or (ii) bipolar disorder I/II (symptomatic or asymptomatic in any phase of the illness); (c) ability to provide written and informed consent; (d) obesity 30 kg/m^2; (e ) weight under 440lbs; (f) shoulder-to-shoulder width under 60 cm; Exclusion criteria are as follows: (a) age below 18 or above 65; (b) use of benzodiazepines or consumption of alcohol within 12 hours of assessments; (c) abuse of marijuana; (d) physical,

cognitive, or language impairments sufficient to adversely affect data derived from assessments; (e) diagnosed reading disability or dyslexia; (f) clinically significant learning disorder by history; (g) history of moderate or severe traumatic brain injury; (h) other neurological disorders, or unstable systemic medical diseases; and (i) pregnancy and post-partum period (j) presence of any contra-indications for MRI; (k) weight above 440lbs; (l) shoulder-to-shoulder width greater than 60 cm. All subjects will be consented prior to initiating the study; (m) >45 BMI; (n) suicidality as determined by clinical discretion.

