#### 2. Illness Measurements:

- a. Severity of depression will be assessed with the Quick Inventory of Depressive Symptomatology (QUIDS)
- b. Measurement of anhedonia composite (SHAPS)
- c. Self-rated cognitive measurement (PDQ-5) Perceived Deficit Questionnaire 5
- d. Objective cognitive measurement (TMTA/B)
- e. Digit Symbol Substitution Test (DSST)
- f. UCLA Loneliness Scale

- g. Food Diary
  - h. Calorimetry
  - i. Anxiety Measurement (Hamilton Anxiety Scale) (HAMD)
  - j. Age of onset
  - k. Number of episodes
  - l. Number of hospitalizations
  - m. Duration of current episode
  - n. Psychiatric comorbidity
  - o. Number of treatments
3. Medical Assessment:
- a. Weight
  - b. Height
  - c. Waist circumference
4. Laboratory Measures:
- a. Blood glucose
  - b. Cholesterol and fractionation (E.g. HDL, LDL and triglycerides)
  - c. Insulin levels
  - d. Interleukin 1, interleukin 6, interleukin 10, tumor necrosis factor alpha, c reactive peptide, adiponectin, leptin, ghrelin, DPP-IV
  - e. Oxidative stress markers (e.g. TBARS)
5. Effort Expenditure for Rewards Task (EEfRT)
6. Monetary Incentive Delay (MID) task
7. Probabilistic Reward Task (PRT)
8. MRI Scan

All assessments and scan will be done on the same day.

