One of the key subcomponents of metabolic dysfunction in obesity is insulin resistance. Insulin resistance has been associated with depressive symptoms in epidemiological studies and, in clinical populations, with anhedonia specifically. Indeed, we observed a strong correlation between insulin resistance and willingness to expend effort in the MDD subgroup. Multiple brain regions that are relevant to reward systems have relatively increased expression of insulin receptors. Specifically, midbrain dopamine neurons, one of the main hubs of reward neurocircuitry, widely express insulin receptors. Imaging studies have reported that, in healthy individuals, insulin modulates brain activity in the hypothalamus, hippocampus and prefrontal cortex. A recent gene expression analysis reported that the differential expression of dopamine-related molecules in individuals with mood and psychotic disorders was related to altered expression of insulin signaling genes; an effect that was moderated by obesity in a region-specific manner (Mansur et al., 2018). As a result, peripheral insulin sensitivity has been shown to modulate reward behavior in humans. In obese adults, insulin resistance was associated with a stronger preference for immediately receiving a smaller, but certain, monetary reward over delaying the receipt of a larger, but less certain one (i.e. greater delay discounting).

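### The plan never states a model for the obesity–effort association that keeps BMI in and the proposed laboratory mediators out; the stepwise regression either tests BMI against those mediators or does not test it.

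*Combined protocol and SAP*

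**What the plan says.** The Statistical Analysis section makes the association of obesity with reward motivation (EEfRT, MID, PRT) a co-primary outcome. The Introduction gives the relation of overweight/obesity to EEfRT effort as the primary aim.

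The same section gives the blood measures a causal position: "Laboratory parameters will be used to explore potential mediational relationships between obesity and brain connectivity measurements, as well as reward performance". Two steps use the effort data.

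- GEE logistic models for choosing the hard task, with group, reward magnitude, probability, expected value and trial number. No laboratory covariate is listed.
- A per-subject analysis: "To assess associations between EEfRT and clinical and metabolic data, we will calculate the mean proportions of hard-task choices for all subjects". It is followed by: "Stepwise linear regression will then be used to identify significant predictors".

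The plan gives no candidate list, direction of selection, entry or removal threshold, or forced term for the stepwise step, and no method for the mediation analysis.

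Primary and Secondary Outcome Measures uses the word metabolic for blood measures: "Metabolic parameters will be measured immediately in a single laboratory with the same assay". The laboratory list under Measurements Obtained at Single Visit includes "Interleukin 1, interleukin 6, interleukin 10, tumor necrosis factor alpha, c reactive peptide, adiponectin, leptin, ghrelin, DPP-IV", besides glucose, lipids, insulin and an oxidative stress marker.

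On the sample, the Participants section says "Twenty subjects with obesity, will be enrolled". The inclusion criterion reads "d) obesity 30 kg/m" squared, and BMI above 45 is excluded.

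**The concern.** A mediator lies on the path from obesity to effort. It is correlated with BMI and carries part of BMI's effect. Once it is in the regression, the BMI coefficient is the direct effect, meaning what is left after the mediated part is removed. The co-primary question concerns the total association. Selection by p-value adds a second problem: whichever of two correlated variables looks stronger in the sample enters first, and the other is then judged on what remains.

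If BMI and the laboratory values are candidates together, the final model could list a laboratory marker and omit BMI because obesity acts through that marker. A reader could take this as no obesity association, while the mediation analysis describes how obesity acts. If BMI is not a candidate, the regression says nothing about obesity and effort, and the estimate has to come from elsewhere in the plan.

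**Working it through.** **1. Which variables are candidates?** The stepwise sentence follows directly on the one about clinical and metabolic data, and the plan calls blood measures metabolic. Laboratory values are therefore the natural candidates. By count, the laboratory list holds about 16: glucose (1), lipids (4), insulin (1), the nine quoted above, and TBARS (1), so 1+4+1+9+1 = 16. Two HOMA2 indices come on top. BMI is neither included nor excluded, so both readings have to be considered.

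**2. Does another planned analysis supply the total association?** The GEE models and the t-tests or Mann-Whitney tests contain no laboratory terms, so mediators do not affect them. Their obesity contrast would be the group term. All 20 participants have obesity and no groups are defined. The Introduction describes the contrast as varying BMI above 30, which is continuous. These analyses therefore do not clearly give the estimate.

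**3. Size of the loss if BMI is a candidate.** The plan states no power, effect size or stepwise rule, so there is no figure of its own to reproduce. The following are assumptions:

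- n = 20; BMI, four laboratory variables and effort all standard normal
- each laboratory variable correlated a = 0.5 with BMI
- true total correlation r, with a share m mediated equally through the four variables
- forward selection with removal, entry p<0.05, removal p>0.10; at least 1,000 samples per setting

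The paths are b = m·r/(4a) from each laboratory variable to effort and c′ = (1−m)·r directly from BMI, so that r = c′ + 4ab. For r = 0.5 and m = 0.5: b = 0.25/2 = 0.125, c′ = 0.25, and 0.25 + 4×0.5×0.125 = 0.50. For m = 1, c′ = 0.

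| True r | BMI alone significant | Kept by stepwise, m=0% | m=50% | m=100% |
|---|---|---|---|---|
| 0.3 | about 25% | 18% | 16% | 13% |
| 0.5 | about 65% | 52% | 40% | 24% |

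With 1,000 samples, the standard error of a figure near 40% is √(0.4×0.6/1000) = 0.015, so differences of two or three points are noise.

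Among samples at r = 0.5 where BMI alone was significant, stepwise lost BMI in about 19%, 38% and 61%. This comparison is made within the same samples, so low power does not explain it.

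**4. Check of the BMI-alone column (Fisher z).** Power = Φ(atanh(r)·√17 − 1.96).

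- r = 0.3: 0.3095×4.123 − 1.96 = −0.684, power 0.25
- r = 0.5: 0.5493×4.123 − 1.96 = 0.305, power 0.62

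Both agree with the simulation.

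**5. Sensitivity.** These figures are the share of samples with BMI significant alone but absent from the stepwise model, with one laboratory variable correlated 0.5 with BMI.

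- r = 0.5, n = 20: about 5% with no mediation, 22% at 25% mediated, 56–58% at 50%, 86% at 80%.
- r = 0.5, half mediated, looser thresholds (0.10/0.15) or backward elimination: 48–49%.
- Half mediated, n = 100: 61% at r = 0.3 and 20% at r = 0.5. The loss is therefore not only a small-sample effect.

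**The case against.** The strongest reply is that the plan never says BMI enters the stepwise regression. A reader might infer that the laboratory variables do compete with BMI there, and that a real association will often drop out. The text supports only that the candidates are unstated. Joint candidacy is an inference, and how often BMI would drop out depends on a mediated share and BMI–laboratory correlations that the documents do not give. This objection stands, and the point is limited accordingly.

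Second, the stepwise step is not declared to be the test of the co-primary association, and the GEE models carry no laboratory terms. That is correct, so it would be wrong to say that the stepwise result decides the co-primary. The reply would settle the matter if the group term meant something, but with every participant obese it has no stated contrast.

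Third, a reader might take insulin resistance to be a pre-named hypothesis that is denied a direct test, because the Implications section says "we observed a strong correlation between insulin resistance and willingness to expend effort in the MDD subgroup". That sentence reports an earlier observation within a discussion. The Introduction's hypotheses do not name insulin resistance. The wording on clinical and metabolic data also suggests that associations are looked at before selection begins, though that step is not specified.

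Fourth, under full mediation BMI has no direct effect, so leaving it out describes the direct effect correctly. A total effect that runs through a mediator, with BMI non-significant given that mediator, is coherent. It misleads only a reader who takes absence from the model as absence of an association. The plan does not invite that reading, but it does not guard against it either.

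Finally, the study is a pilot and the analysis is called preliminary and exploratory. That lowers the stakes but does not settle which quantity is being estimated.

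**Conclusion.** The concern holds in a limited form. The plan does not state a usable model for the total association of obesity with effort. The stepwise step tests BMI conditionally on its proposed mediators if BMI is a candidate, and does not address it if BMI is not. The analyses without laboratory terms rely on undefined groups.

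Under the assumptions above, at n = 20 and r = 0.5, retention falls from about 65% to 40% with half the effect mediated and to 24% with all of it. At r = 0.3 the fall is from about 25% to 16% and 13%, that is 9 and 12 points, and low power dominates. The fall at 0% mediation (65% to 52%, and 25% to 18%) is ordinary collinearity and selection and should not be attributed to mediation. With one laboratory variable and little or no mediation the loss is small.

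The documents do not show that BMI will be dropped, and the figures are conditional illustrations. Low power at n = 20 is a separate limit that this correction does not remove: by Fisher z, 80% power needs ((1.96+0.84)/atanh(r))² + 3, which is about 85 participants at r = 0.3 and 30 at r = 0.5.

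**What to change.** In the Statistical Analysis section:

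1. Estimate the obesity–effort association with continuous BMI forced into a model that contains no laboratory variable. Report the coefficient with its confidence interval, whatever the p-value.
2. Put BMI and laboratory variables together only in models labelled exploratory mediation, and name the method, for example an indirect effect with a bootstrap interval.
3. Keep BMI out of stepwise selection. If the stepwise step is retained, list its candidates and its entry and removal rules, and label the result descriptive.
4. State that the absence of BMI from a stepwise model is not evidence against an obesity association.

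Laboratory variables need not be removed from a descriptive stepwise step. A separate model for HOMA2 insulin resistance is optional.

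The cost is SAP wording and a few extra regressions on data already planned. No new measurement or participant is needed.

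### The normality test that chooses between t-test and Mann-Whitney is too insensitive at n = 20 to do that job unless it is corrected for estimated parameters

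*Combined protocol and SAP*

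**What the plan says.** The Statistical Analysis section sets a two-step rule. First, "For each variable, distribution normality will be assessed with one-sample Kolmogorov-Smirnov tests". Then group comparisons use "independent samples t-tests and Mann-Whitney U (for normally and non-normally distributed variables, respectively").

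The section does not give the reference mean and SD, any correction for estimating them, the level of the normality test, or whether the test is run on all participants together or within each group.

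The Participants section says "Twenty subjects with obesity, will be enrolled". All must be obese, and no comparison group is defined. The laboratory list includes insulin, glucose and lipids, and also "Interleukin 1, interleukin 6, interleukin 10, tumor necrosis factor alpha, c reactive peptide, adiponectin, leptin, ghrelin, DPP-IV".

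The stated uses of the laboratory data are mainly elsewhere in the Statistical Analysis section: "Laboratory parameters will be used to explore potential mediational relationships between obesity and brain connectivity measurements, as well as reward performance". For clinical and metabolic associations with the EEfRT, "Stepwise linear regression will then be used to identify significant predictors".

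**The concern.** The standard Kolmogorov-Smirnov critical values hold only when the reference distribution is fixed in advance. Here no reference is fixed. The mean and SD must come from the same 20 values, which pulls the fitted curve towards the data and makes the test statistic too small for the tabulated cut-off. The test then passes variables that it should flag.

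It matters because this is the only distributional check in the plan. Insulin, triglycerides, CRP and cytokines are plausibly right-skewed. If they pass, they are compared with a t-test on the raw scale, where a few large values inflate the standard error. With 20 participants there is little power to spare.

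**Working it through.** The plan states no rejection rate, power, level or effect size, so there is no figure of its own to reproduce. The check is by simulation.

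**Inputs from the documents.** n = 20 (Participants); one-sample Kolmogorov-Smirnov test, then t-test or Mann-Whitney (Statistical Analysis).

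**Assumed, because the documents give nothing.** Two-sided 5% for both steps; lognormal variables with log-SD 0.5 to 1.5; equal-variance t-test; a shift of 1 SD on the log scale; splits of 10 v 10 and 14 v 6.

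**Step 1: the cut-off.** With z = (x − sample mean)/sample SD, sorted, and Φ the normal distribution function, D = max over i of {i/n − Φ(z_i), Φ(z_i) − (i−1)/n}. At n = 20 the ordinary 5% cut-off is D = 0.294. When mean and SD are estimated, the cut-off that really gives 5% (Lilliefors, simulated) is 0.192. A fixed standard normal reference is not workable either: raw values with mean 5 and SD 1 were rejected in every sample.

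**Step 2: how often normality is rejected at n = 20** (20,000 samples per row; 4,000 for Shapiro-Wilk).

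| Distribution | Uncorrected KS | Lilliefors | Shapiro-Wilk |
|---|---|---|---|
| Normal | 0.0% | 5% | 5% |
| Lognormal, log-SD 0.5 | 1.4% | 34% | 52% |
| log-SD 0.8 | 10% | 65% | 84% |
| log-SD 1.0 | 20% | 79% | 93% |
| log-SD 1.5 | 52% | 96% | 99% |

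**Step 3: power of the whole rule, 10 v 10**, test applied to the pooled 20 values (10,000 trials per row). Loss = Mann-Whitney minus rule.

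| log-SD | Always t | Rule, uncorrected KS | Always Mann-Whitney | Loss (points) | Rule, Lilliefors | t on logs |
|---|---|---|---|---|---|---|
| 0.5 | 50.3% | 50.6% | 51.3% | 0.7 | 51.6% | 56.5% |
| 0.8 | 42.5% | 45.7% | 51.3% | 5.6 | 50.9% | 56.2% |
| 1.0 | 37.2% | 45.0% | 51.6% | 6.6 | 51.1% | 56.6% |
| 1.2 | 31.1% | 44.6% | 51.2% | 6.6 | 50.9% | 56.0% |
| 1.5 | 23.3% | 46.9% | 51.9% | 5.0 | 51.8% | 56.3% |

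If the test is instead run within each group of 10, the losses down the rows are about 1, 8, 12, 16 and 19 points.

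**Step 4: power with 14 v 6**, pooled test (20,000 trials per row), rule v Mann-Whitney.

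| log-SD | Larger group higher | Smaller group higher |
|---|---|---|
| 0.8 | 27% v 43% | 49% v 43% |
| 1.0 | 25% v 43% | 46% v 43% |
| 1.2 | 25% v 43% | 45% v 43% |
| 1.5 | 30% v 43% | 44% v 43% |

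Before rounding, the losses in the first column are 15.6, 17.8, 17.1 and 13.0 points. The asymmetry arises because the higher group also has the larger raw-scale variance. When that group is the larger one, the pooled variance is overstated.

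**Step 5: type I error.** With no shift, the 10 v 10 rule rejects 3.3% to 4.5% of the time, counting both pooled and within-group testing.

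**The case against.** The strongest objection is that the t-test route cannot be carried out as the plan stands, because no second group exists among 20 obese participants. A reader might fill the gap with depression versus bipolar disorder. The eligibility criteria list those only as alternative ways to qualify, and no comparison between them is planned. This stands, and it makes every power figure above conditional on an assumed split. It does not rescue the rule: the plan still announces group comparisons and ties the choice of test to this check.

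Second, the software may apply Lilliefors, which the plan neither states nor excludes. If it does, power at 10 v 10 is within about 1 point of always using Mann-Whitney. This also stands, and is a reason to specify the version.

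Third, a reader might infer three stronger claims, which the documents and figures do not support:

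- *The test almost never rejects.* This is true for mild to moderate skew only. At log-SD 1.5 even the uncorrected version rejects 52%.
- *The loss at log-SD 1.0 is 37% v 52%.* That compares always using the t-test with always using Mann-Whitney. The planned rule diverts some skewed samples to Mann-Whitney, and the comparison is 45% v 52%.
- *The normality test distorts the regression and mediation results.* It governs only the t-test/Mann-Whitney choice. Linear regression does not need normally distributed predictors. The missing transformation rule there is a separate gap.

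Finally, the study describes itself as exploratory, and the EEfRT choices are modelled by logistic GEE, which this rule does not touch. That limits the weight of the point.

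**Conclusion.** The point holds in limited form. As written, and without a correction, the normality test has a true level near 0% at n = 20 and passes about 99%, 90% and 80% of lognormal samples with log-SD 0.5, 0.8 and 1.0.

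The consequence is lost power, not false positives. It is negligible at log-SD 0.5 and about 5 to 7 points at log-SD 0.8 to 1.5 with equal groups and a pooled test. It is larger if the test is run within groups, or if the groups are unequal and the larger one is higher. With the smaller group higher, the rule is slightly better than Mann-Whitney. The plan cannot know which case will apply.

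All of this rests on assumed distributions, splits, levels and effect size. It is a modest point, worth correcting because the correction is nearly free. The undefined groups are the more basic gap.

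**What to change.** In the Statistical Analysis section:

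1. Delete the Kolmogorov-Smirnov step. Pre-specify Mann-Whitney, or a t-test on log values, for group comparisons of laboratory variables expected to be right-skewed, such as insulin, triglycerides, CRP and cytokines. List the variables before the data are seen.
2. If a preliminary test is kept, at minimum replace it with Lilliefors or Shapiro-Wilk. State its level and whether it is run on all participants or within groups.
3. Name the groups being compared, or remove the group comparisons.
4. Separately, for the regression and mediation analyses, state that skewed laboratory predictors are log-transformed and that residuals are checked.

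The cost is a few sentences, with no new data or design change. The downside is some efficiency lost by Mann-Whitney where a variable really is normal. The log-scale column in the 10 v 10 table shows its size, since those logged values are exactly normal: about 56% power for the t-test against 51% to 52% for Mann-Whitney.
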